9.1.9. Study and Site Closure

The sponsor may suspend or terminate the study or part of the study at any time for any reason. If the investigator suspends or terminates the study, the investigator will promptly inform the sponsor and the IRB/IEC and provide them with a detailed written explanation. Upon study completion, the investigator will provide the sponsor, IRB/IEC, and regulatory agency with final reports and summaries as required by regulations. Study termination and follow-up will be performed in compliance with the sponsor or designee standard operating procedures.

The sponsor, investigator, or local and national regulatory authorities may discover conditions during the study that indicate that the study or study site should be terminated. This action may be taken after appropriate consultation between the sponsor and investigator. Conditions that may warrant termination of the study/study site include, but are not limited to:

- The discovery of an unexpected, serious, or unacceptable risk to the subjects enrolled in the study.
- The decision on the part of the sponsor to suspend or discontinue testing or evaluation of the study drug.
- Failure of the investigator to enroll subjects into the study at an acceptable rate.
- Failure of the investigator to comply with pertinent regulations.
- Submission of knowingly false information from the study site to the sponsor, study monitor, or local and national regulatory authorities.
- Insufficient adherence to protocol requirements.

9.1.10. Publication Policy

The sponsor's decision to publish or otherwise publicly communicate the results of this study will be made in accordance with all applicable laws, regulations, and sponsor policies regarding publication and communication of clinical study results.

Terms and provisions of the investigator's publication rights are governed by the Publication Section in the Clinical Trial Agreement per site.

9.2. Appendix 2: Clinical Laboratory Tests

Serum Chemistry:	
Alanine aminotransferase (ALT)	Chloride
Albumin (total)	Creatinine
Alkaline phosphatase	Glucose
Aspartate aminotransferase (AST)	Phosphorus
Bilirubin (total)	Potassium
Blood urea nitrogen	Protein, total
Calcium	Sodium
Bicarbonate	Uric acid
Lipid Profile:	
High density lipoprotein	Triglycerides
Low density lipoprotein	Total cholesterol
Hematology Assays:	
Hematocrit	White blood cell count, including differential
Hemoglobin	Platelet count
	Red blood cell count
Urinalysis:	
Color	Ketones
Clarity	Protein
Albumin	pH
Bilirubin	Specific gravity
Blood	Urea
Creatinine	Microscopy (WBC/ high power field (HPF), RBC/HPF and urinary casts)
Glucose	
Diabetes Screen:	
	HbA1c
Hormones:	
Serum and urine beta-human chorionic gonadotropin (pregnancy test)	Thyroid Stimulating Hormone
Hepatitis and HIV Serology:	
Hepatitis B core antibody	Hepatitis C virus antibody (HCV)
Hepatitis B surface antigen	Human immunodeficiency virus (HIV)
TB Assay:	
Immunological protein assay:	
	Protein assay to detect levels of the cytokine array [interleukin 1,6,17; interferon- γ]; ratio of T helper cells to T regulatory cells

9.3. Appendix 3: Adverse Events: Definitions and Procedures for Recording, Evaluating, Follow-Up and Reporting

9.3.1. Safety

For safety information about Acthar, refer to the most recent version of the Prescribing Information (Mallinckrodt Package Insert, 2019).

9.3.2. Definitions

Adverse Event

An AE is any untoward or undesirable medical occurrence in a subject who is administered a study treatment, which does not necessarily have to have a causal relationship with this treatment. Examples of AEs include but are not limited to:

- Clinically significant laboratory findings.
- Clinically significant changes in physical examination findings.
- An AE occurring due to study drug overdose whether accidental or intentional.
- An AE occurring from study drug abuse.
- An AE associated with study drug withdrawal.
- Unexpected Adverse Event.

An unexpected AE is defined as an AE, the nature and severity of which is not consistent with the applicable product information in the most recent version of the Prescribing Information (Mallinckrodt Package Insert, 2019).

Serious Adverse Event

An SAE is defined as any untoward medical occurrence that at any dose results in any of the following outcomes:

- Death.
- Life-threatening AE.
- Inpatient hospitalization or prolongation of existing hospitalization.
- A persistent or significant incapacity or substantial disruption of the ability to conduct normal life functions.
- Results in a congenital anomaly/birth defect.

Death

Death is an outcome of an event. The cause of death should be recorded and reported on the SAE Form. All causes of death must be reported as SAEs. The investigator should make every effort to obtain and send death certificates and autopsy reports to the sponsor or designee, or state not available.

Life-Threatening Event

An adverse event or suspected adverse reaction is considered "life-threatening" if, in the view of either the investigator or sponsor, its occurrence places the subject at immediate risk of death. It does not include an adverse event or suspected adverse reaction that, had it occurred in a more severe form, might have caused death. For example, hepatitis that resolved without evidence of hepatic failure would not be considered life threatening, even though hepatitis of a more severe nature can be fatal. Similarly, an allergic reaction resulting in angioedema of the face would not be life threatening, even though angioedema of the larynx, allergic bronchospasm, or anaphylaxis can be fatal.

Hospitalization

Hospitalization is defined as an official admission to a hospital. Hospitalization or prolongation of a hospitalization constitutes a criterion for an AE to be serious. The following situations should not be reported as SAEs:

- A hospitalization or prolongation of hospitalization is needed for a procedure required by the protocol.
- A hospitalization or prolongation of hospitalization is part of a routine procedure followed by the center (eg, stent removal after surgery). This should be recorded in the study file.
- A hospitalization for a preexisting condition that has not worsened.

Important Medical Events

Important medical events that may not result in death, be life threatening, or require hospitalization may be considered serious when, based upon appropriate medical judgment, may jeopardize the subject and may require medical or surgical intervention to prevent one of the outcomes listed above. Examples of such medical events include allergic bronchospasm requiring intensive treatment in an emergency department or at home, blood dyscrasias or convulsions that do not result in inpatient hospitalization, or the development of drug dependency or drug abuse.

AEs (serious or non-serious) that commonly occur in the study population or background regimen will be considered anticipated events. Such events include known consequences of the condition under investigation (eg, symptoms, disease progression) and other events that may be common in this study population. Anticipated events are to be recorded on the eCRF and reported as SAEs when serious. These SAEs will not be expedited to health authorities, but included in aggregate safety reports.

9.3.3. Adverse Event and Serious Adverse Event Classifications

Study Drug Relatedness

The following classifications should be used when evaluating the relationship of AEs or SAEs to study treatment.

Table 3: Adverse Event Relationships

Relationship	Definition
Not Related	No relationship between the AE and the administration of study treatment; the AE cannot be explained by other etiologies such as concomitant medications or subject's clinical state.

Relationship	Definition
Unlikely Related	The current state of knowledge indicates that a relationship to study treatment is unlikely.
Possibly Related	An AE that follows a plausible temporal sequence from administration of the study treatment to the start of the AE and follows a known response pattern to the suspected study treatment. The reaction might have been caused by the subject's clinical state or concomitant medications.
Related	The AE that follows a plausible temporal sequence from administration of the study treatment to the start of the AE and follows a known response pattern to the study treatment. The suspected causality can be confirmed with a positive re-challenge test or supporting laboratory data.

Severity Assessment

For purposes of consistency, the investigator may use the intensity grades presented in the following table, if required:

Table 4: Adverse Event Severity Grades

Grade	Definition
Mild	Does not interfere with subject's usual function and activities
Moderate	Interferes to some extent with subject's usual function and activities
Severe	Interferes significantly with subject's usual function and activities

To ensure there is no confusion or misunderstanding of the difference between the terms “serious” and “severe,” which are not synonymous, the following note of clarification is provided:

The term “severe” is used to describe the intensity (severity) of a specific event (as in mild, moderate, or severe myocardial infarction); the event itself, however, may be of relatively minor medical importance (such as a severe headache). This is not the same as “serious,” which is based on the subject/event outcome or action criteria usually associated with events that pose a threat to a subject's life or functioning. Seriousness (not severity) serves as a guide for defining regulatory reporting obligations.

If an AE increases in severity (eg, from moderate to severe); decreases in severity (eg, changes from moderate to mild); or if there is a change in seriousness, a new AE will be opened and the original AE will be closed. If an AE is still ongoing at the time of a subject's completion of the follow-up visit, the resolution/stop date and time is left blank.

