8.3.2. Safety Analyses

All safety data will be summarized with descriptive statistics or frequency tables as appropriate. Safety analyses will be performed on the safety population. Safety endpoints include the incidence and severity of ocular AEs, incidence and severity of other AEs, new or worsening cataracts, and the mean change in IOP.

AEs will be coded using MedDRA version 22.0 by preferred term within system organ class. The number of AEs and the number of subjects reporting AEs will be listed and summarized descriptively by system organ class, preferred term, severity, and causality for each treatment group. Only treatment-emergent adverse events (TEAE) (events that are new in onset or aggravated in severity following treatment) will be included in all summaries. Serious adverse events (SAE) (including death) will be summarized.

Other safety assessments include vital signs (heart rate, diastolic/systolic blood pressures, respiratory rate, and body temperature), clinical laboratory tests, ophthalmology examinations, physical examinations, HbA1c, pregnancy test, hepatitis serology, IGRA for TB, etc. All of these assessments will be listed and summarized descriptively.

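### In Table 3 the second clause of the Not Related definition is reversed and contradicts the first, so causality will be assigned inconsistently, mainly between Not Related and Unlikely Related

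*Combined protocol and SAP*

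**What the plan says.** Section 9.3.3 introduces Table 3 as the scale for causality: "The following classifications should be used when evaluating the relationship of AEs or SAEs to study treatment". The severity grades in the same section are worded as optional; the causality categories are not.

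The four categories rest on these statements:

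- *Not Related*, first clause: "No relationship between the AE and the administration of study treatment".
- *Not Related*, second clause: "the AE cannot be explained by other etiologies such as concomitant medications" or the subject's clinical state.
- *Unlikely Related*: "The current state of knowledge indicates that a relationship to study treatment is unlikely".
- *Possibly Related*: plausible timing and a known response pattern, and "The reaction might have been caused by the subject's clinical state or concomitant medications".
- *Related*: plausible timing and a known response pattern, and "The suspected causality can be confirmed with a positive re-challenge test or supporting laboratory data".

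Section 8.3.2 uses the result. AEs are to be listed and "summarized descriptively by system organ class, preferred term, severity, and causality for each treatment group".

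**The concern.** An identified alternative cause is a reason to call an event unrelated to the drug. The lack of one is, if anything, a reason to suspect the drug. The second clause of *Not Related* makes the lack of an alternative part of the definition, so it works against both the label and the first clause. It reads as if *cannot* was written for *can*.

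Safety is part of the stated objective (Section 2). The study is open-label and not randomized (Section 5.4), so there is no concurrent background AE rate, and no monitoring committee is used (Section 9.1.5). A table of AEs by investigator causality will be read with that in mind, and it is only as good as the definitions behind it. Recognizing a suspected unexpected serious adverse reaction, which Section 9.3.4 mentions, also depends on a judgment of relatedness.

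**Working it through.** No arithmetic applies, and the plan has no figure to reproduce. The check takes the definition clause by clause and then traces where causality is used.

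**Step 1: which events fit *Not Related*.** Clause 1 is no drug relationship. Clause 2 is that other causes cannot explain the event. As written, both must hold. The last two columns show two possible repairs.

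| Event | Clause 1 | Clause 2 | Fits as written | Fits if clause 2 is deleted | Fits if *cannot* becomes *can* and both clauses are still required |
|---|---|---|---|---|---|
| A. No drug relationship, clear other cause | met | not met | no | yes | yes |
| B. No drug relationship, no other cause found | met | met | yes | yes | no |
| C. Drug relationship suspected, no other cause found | not met | met | no | no | no |
| D. Drug relationship suspected, other cause also possible | not met | not met | no | no | no |

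Row A is the fault. The clearest kind of unrelated event is shut out. Such events are foreseen: Section 9.3.2 describes anticipated events that follow from the disease itself, and those are explained by clinical state.

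Row C shows the limit of the fault. An event with no other explanation meets clause 2 but still fails clause 1, so it does not become *Not Related*.

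**Step 2: where row A events go.** *Unlikely Related* says nothing about alternative causes and is the natural next category. *Possibly Related* does mention clinical state and concomitant medications, but it also requires plausible timing and a known response pattern, and the faulty clause does not change those conditions. Some leakage there is possible for events of a type listed in Section 1.3, such as raised blood pressure, when the timing also fits. The documents do not show how often that would occur.

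**Step 3: where causality is used.**

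- Used: the AE summary by causality in Section 8.3.2, and any sponsor judgment that depends on relatedness.
- Not used: recording of AEs and serious AEs, which Section 9.3.4 requires whatever the relationship; 24-hour reporting of serious AEs to the sponsor (Table 5); the treatment-emergent definition and total counts (Section 8.3.2); the named safety endpoints, which are AE incidence and severity, cataracts and IOP change (Section 8.3.2); the AEs of special interest (Section 9.3.5); and the primary IDEEL responder outcome (Section 2.3).

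**Step 4: whether anything corrects it.** No other section restates or corrects the definition.

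**The case against.** The strongest reply is that investigators will follow the category name and the first clause, both of which are right, and will read past an obvious slip. Most row A events would then be coded *Not Related* after all. Even under a literal reading they would mostly land in *Unlikely Related*, which is still on the unrelated side. Causality is one of several descriptive breakdowns, and Section 2.2 looks for safety signals through AE frequency, laboratory tests, vital signs and ophthalmic findings.

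Most of this stands, and it limits the size of the point. It does not remove it. If some investigators follow the label and others follow the text, similar events receive different codes. The sentence is complete and grammatical, so nothing suggests a fault in reading the PDF.

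A reader might go further and infer that the whole definition is backwards and that the causality summary will be built on inverted coding. The documents do not support that. Nothing swaps the categories, the other three definitions point the right way, and row C shows that an unexplained event is not pulled into *Not Related* unless the investigator also finds no drug relationship. Nor is every event with an alternative cause affected: one that meets the timing and pattern conditions belongs in *Possibly Related*, which already allows for another cause.

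**Conclusion.** Wrong as written; minor severity. The second clause of *Not Related* contradicts the first, and the expected result is inconsistent assignment, mainly between *Not Related* and *Unlikely Related*. The effect is confined to the AE-by-causality summary and to sponsor judgments that rest on relatedness.

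Its size cannot be put as a count, because the documents give neither an AE rate nor the share of events with an alternative cause. The conclusion assumes that both clauses must hold, as the wording implies, and that no other instruction to sites overrides Table 3. Any eCRF completion instructions are not among the documents, so their wording could not be checked.

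**What to change.** 1. In Table 3, delete the second clause of *Not Related*. Alternatively, reword it so that another cause supports the category without being a condition, for example: *another cause, such as a different medicine or the underlying disease, may account for the event but need not be identified*. Changing *cannot* to *can* and still requiring both clauses is not enough: it would shut out unrelated events of unknown cause (row B).
2. Use the same text in any eCRF completion instructions.
3. If AEs have already been classified, review the *Not Related* and *Unlikely Related* assignments before database lock.

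The cost is one line of text. Section 9.1.1 requires an amendment for any change to the study plan, so the correction can go in with the next one. The review in step 3 costs some site and medical monitor time, and only if coding has begun.

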2.2. Assessment of Safety

The frequency of adverse events (AEs), AEs of special interest (AESIs); clinical laboratory tests; metabolic panel; vital signs; physical examination; and ophthalmic findings (best corrected visual acuity, intraocular pressure, slit lamp examination, undilated eye examination) will be used to detect the presence of a safety signal(s).

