9.3.4. Adverse Event and Serious Adverse Event Recording and Reporting

AEs and SAEs will be recorded from signing of the ICF through completion of the Follow-up Visit. The investigator is required to record the AE or SAE regardless of the severity of the event or its relationship to study treatment. The investigator must follow up on all AEs and SAEs reported to have occurred through the Follow-up Visit until the event has resolved or stabilized or at such time the investigator refers the subject to a nonstudy physician. The investigator will document the further follow-up information in the subject's source document.

During the period specified above, the investigator will:

- Record all AEs and SAEs from the signing of the ICF through the completion of the Follow-up Visit.
- Report all SAEs on an SAE Report Form to Mallinckrodt Global Pharmacovigilance or designee.
- Report all pregnancies to Mallinckrodt Global Pharmacovigilance or designee on the appropriate form.
- Submit any Expedited Safety Report or Suspected Unexpected Serious Adverse Reaction from Mallinckrodt Global Pharmacovigilance or designee to the IRB/IEC.

The reporting requirements for AEs are summarized in the following table:

Table 5: Reporting Requirements for Adverse Events

Seriousness	Reporting Time	Type of Report
All Serious	Within 24 hours of first knowledge of event	Initial report on the SAE Form, appropriate eCRF, and source document
	Within 24 hours of receipt of follow-up information	Follow up report on the SAE Form, appropriate eCRF, and source document
Nonserious	Per case report form submission procedure	Appropriate eCRF and source document

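### Table 3 makes a known response pattern a condition of both positive causality grades, so a well-timed reaction of a new type has no fitting positive category

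*Combined protocol and SAP*

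**What the plan says.** Section 9.3.3 introduces Table 3 as the scale to apply: "The following classifications should be used when evaluating the relationship of AEs or SAEs to study treatment". It has four levels.

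- Possibly Related needs a plausible time course "to the start of the AE and follows a known response pattern to the suspected study treatment". It allows that the subject's condition or other medication might have been the cause.
- Related needs a plausible time course "to the start of the AE and follows a known response pattern to the study treatment". It adds that causality can be confirmed by rechallenge or laboratory data.
- Unlikely Related reads: "The current state of knowledge indicates that a relationship to study treatment is unlikely".
- Not Related requires that there be no relationship to study treatment. It goes on to say that other causes cannot explain the event, which looks inverted.

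Section 9.3.2 defines an unexpected AE as one "the nature and severity of which is not consistent with the applicable product information", with the Prescribing Information as reference. Section 8.3.2 plans to summarise AEs "by system organ class, preferred term, severity, and causality for each treatment group". Section 9.3.4 gives the site this duty: "Submit any Expedited Safety Report or Suspected Unexpected Serious Adverse Reaction". Such reports are described there as coming from the sponsor's pharmacovigilance group, for the site to pass to the ethics committee.

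**The concern.** A causality scale should let an investigator record reasonable suspicion about something not seen before. In Table 3 even the grade meant for uncertainty asks for prior knowledge of how the drug behaves. An investigator who follows it literally has no positive grade for an event with clear timing, no obvious other cause and no precedent.

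This matters more than usual here. The study is open-label with no randomisation (5.4), there is no comparison group, and no monitoring committee is used (9.1.5). Event frequency alone cannot separate drug effects from disease or background, so readers will lean on the causality columns. For nonserious events, which go only through the case report form and source documents (9.3.4), the Table 3 grade is the only attribution that the protocol describes.

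The wording in 9.3.2 is a second, smaller problem. If nature and severity must both depart from the label, a labelled reaction that is far worse than labelled would not count as unexpected.

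**Working it through.** The plan gives no figure on this point and no arithmetic applies. The check sets the definitions side by side.

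**Step 1. Test a plausibly timed event of a new type, with a positive rechallenge, against each row of Table 3.**

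| Row | What it requires | Met? |
|---|---|---|
| Related | plausible timing and known pattern; rechallenge may confirm | No: the pattern is missing, and rechallenge is added to that condition rather than replacing it |
| Possibly Related | plausible timing and known pattern | No: the pattern is missing |
| Unlikely Related | current knowledge points against a relationship | Not clearly: absence of precedent is not evidence against |
| Not Related | no relationship | No on its first clause; the second clause, on other causes not explaining the event, would take it in if read alone |

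The condition is in two of the two positive rows, and no positive row is free of it. The event falls into a gap. Whichever grade the site then chooses, the only departures from the positive rows are towards non-attribution, so the error has one direction.

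**Step 2. Compare Table 3 with the definition of unexpected in 9.3.2.**

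| Plausibly timed event | Positive grade available? | Unexpected? |
|---|---|---|
| Labelled type, labelled severity | Yes | No |
| Labelled type, greater severity | Yes | Only if a mismatch in either nature or severity is enough |
| Unlabelled, but in line with known pharmacology | Yes if the pattern is judged on pharmacology; no if judged on the label | Yes, since the label does not describe it |
| New type, no known pattern | No | Yes |

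The last line is the defect in Table 3. The second line is the ambiguity in 9.3.2. The third shows that the result depends on what counts as known, which Table 3 does not say.

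**Step 3. Trace where the grade is used.**

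- Recording of AEs and SAEs (9.3.4): independent of relationship.
- SAE reporting to the sponsor (9.3.4, Table 5): all serious events within 24 hours, with no relatedness filter.
- Basis for signal detection (2.2): frequency of AEs and AEs of special interest, plus laboratory, vital-sign, physical and ophthalmic findings; causality is not mentioned.
- AE summaries (8.3.2): all treatment-emergent events, defined by onset or worsening; causality is one classification variable.

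The grade therefore acts directly on the summaries by causality, and indirectly on the investigator opinion that reaches the sponsor with an SAE.

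**Step 4. Check whether correcting the Not Related row would be enough.** It would not. With its second clause reversed, the novel event still fails both positive rows.

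**The case against.** The strongest counter-argument is that little in the safety system hangs on the Table 3 grade. Every SAE reaches the sponsor within 24 hours whatever the grade, expedited reports originate with the sponsor, all treatment-emergent events are tabulated, and the sponsor's medical monitor reviews the data for safety (9.1.7). All of that stands.

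A reader might go further and infer that no event can be both unexpected and at least possibly related, so that the route to a suspected unexpected serious reaction, and signal detection with it, is closed by definition. The documents do not support this, for three reasons.

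- It equates a known response pattern with the product information. Only the definition of unexpected is tied to the label. Sections 1.1 and 1.2 describe the drug's pharmacology, and an unlabelled event that fits it could be graded positive.
- It takes the 'and' in 9.3.2 as requiring two mismatches. It is just as natural to read the pair as failing to match when either part differs. A labelled reaction of greater severity would then be unexpected and could also be graded related.
- Nothing binds the sponsor to the site's grade. The protocol neither describes nor rules out a causality assessment by the sponsor.

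A reader might also infer that a novel event must be graded Unlikely or Not Related. That is too strong, because neither row clearly fits it. The defect is a missing category.

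What survives the objection is that the prescribed scale has no positive grade for a novel, well-timed event, and that the planned summaries by causality inherit this.

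**Conclusion.** The point holds as a defect in the causality scale, with a secondary ambiguity in the definition of unexpected. Applied as written, Table 3 biases the investigator's grade and the summaries by causality in 8.3.2 away from attributing novel reactions to the drug. Its extent is structural (both positive grades carry the condition), and the documents give no basis for estimating how many events would be affected.

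The conclusion assumes that sites apply Table 3 literally, which 9.3.3 tells them to do, and that an event of a new type has no pattern that the investigator would regard as known. The 9.3.2 point assumes only that the stricter reading is possible.

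This should be corrected, but it is not critical: SAE reporting, inclusion of treatment-emergent events, overall signal detection and the primary outcome are unaffected.

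**What to change.** Three wording changes by amendment, carried into the case report form completion guidance:

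1. Table 3, Possibly Related: define as plausible timing with a reasonable possibility of a causal relationship, whether or not the event follows a known response pattern and even if another cause is possible.
2. Table 3, Related: list a known response pattern as one form of supporting evidence, alongside rechallenge and laboratory data, and not as a condition.
3. Section 9.3.2: write 'nature or severity'.

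Two additions are worth making at the same time. Correct the apparently inverted second clause of Not Related, and state in 9.3.4 whether the sponsor assesses causality independently of the site.

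The cost is the amendment text and site guidance. Somewhat more events will be graded possibly related, and some more SAEs will need expedited assessment. Visits, endpoints and sample size are unchanged.
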